The non-vitamin K oral anticoagulants (NOACs) are a new group of drugs which have been recently approved for use as blood thinners. They have a faster onset of action compared to warfarin and unlike warfarin, they do not need frequent monitoring. Apixaban and Rivaroxaban both have a similar mechanism of action. They inhibit Factor 10 which a clotting factor. They are the most commonly prescribed NOACs at Einstein Medical Center Philadelphia. We intend to serially monitor the kidney function by measuring the serum creatinine and urinalysis of 40 high risk patients who are recently started on either apixaban or rivaroxaban over a six month period. This will enable us to discover what proportion of patients actually develop ARN after starting a NOAC.

2) Project Objectives and Hypotheses:

Determine the incidence of ARN in high risk patients on rivaroxaban or apixaban (Factor 10 inhibitors).

Hypothesis - the incidence of ARN with apixaban or rivaroxaban is less than the previously reported incidence of ARN in warfarin.

- Describe demographic and urinalysis-associated predictors of ARN in patients on rivaroxaban or apixaban (Factor 10 inhibitors)

3) Background/Significance of Research (*Provide the scientific or scholarly background and rationale for the research based on the existing literature (include references). Describe relevant prior experience and gaps in current knowledge. Describe any relevant preliminary data. Explain the significance of the research in terms of why it's important and how it will add to existing knowledge.*):

Anticoagulation-related nephropathy (ARN) is an understudied renal complication of anticoagulant therapy that is characterized by acute kidney injury (AKI) defined as an increase in baseline serum creatinine ≥ 0.3 mg/dL, without any alternate etiology, in the setting of a supra-therapeutic International Normalized Ratio (INR) greater than 3.0 [1-7]. ARN has mainly been studied in relation to warfarin, it usually occurs in the first two months of starting anticoagulant therapy and retrospective studies have estimated the prevalence to range from 16% to 37% [4-6]. The strongest risk factor for ARN is pre-existing chronic kidney disease (CKD); other risk factors include older age, diabetes mellitus and hypertension [1,4]. Patients with ARN have an accelerated progression of CKD and a retrospective study of more than 15,000 patients on warfarin showed a 65% increase in mortality in patients with ARN [4,6].

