- Montgomery campus
- Other: please specify -

b. Indicate if human research will be conducted at external location(s) overseen by the AEHN investigator (e.g. private physician office, collaborating hospital/university)

- Yes (Complete Appendix B: External Site Approvals on Application for Human Research)
- No

5) Resources available to conduct the Human Research:

a. Target population (e.g. Adult subjects with a diagnosis of Type II diabetes for greater than two years?": Elderly patients with CKD who have recently been started on Rivaroxaban or Apixaban

b. For prospective studies:

- i.) Total number of subjects planned to be enrolled in the study at AEHN site(s): 40
- ii) For multi-site projects, please indicate total number of subjects planned to be enrolled in the study at all sites: 0
- iii) Describe access to a population that would allow recruitment of the targeted number of subjects (*i.e. how many potential subjects do you have access to? What percentage of those potential subjects do you need to recruit?*) : We estimate that around 100 patients meeting our criteria are started on Apixaban or Rivaroxaban in a six-month period. We anticipate to recruit 40% (40) of them into the study

c. For retrospective studies:

- i.) Estimated number of charts to be reviewed: N/A
- ii.) Time period of interest for data being collected (*e.g. Subjects who had XX procedure between 6/1/00 and 6/1/05*): N/A

d. Describe the number and qualifications of the study team members, their experience in conducting research, their knowledge of the local study site(s), culture, and society:

Principal Investigator: [name] is a first year intern in Internal Medicine at Albert Einstein Medical Center. [name] completed her medical school training at the University of Jordan in Jordan where she graduated top of her class. She completed a graduate degree in Public Health at Thomas Jefferson University in Philadelphia and she is interested in population epidemiology and determinants of health. At Einstein, he has been very keen to work on research projects with collaboration with other colleagues on various projects

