- i. Describe steps that will be taken to secure the data (e.g. training, authorization of access, password protection, encryption, physical controls, certificates of confidentiality and separation of identifiers and data) during storage, use and transmission: As stated above, a study participant list containing identifiable data will be password protected and stored on the Einstein system. This list will only be able to be accessed by members of the research team. All other data will be stored in a separate database with unique but unidentifiable identification numbers. At the termination of the study the initial study participant list will be deleted.
- ii. Describe the data analysis plan, including any statistical procedures and method for determining the sample size for the study:

Incidence of ARN is the primary outcome of this study and this is based on a documentation of AKI (defined as an increase in baseline serum creatinine ≥ 0.3 mg/dL), in the absence of any other obvious etiology for the AKI identified after a standard clinical evaluation and work up by the patient's primary care physician, cardiologist or nephrologist. This incidence will be expressed as a percentage.

Urinalysis measurements (particularly hematuria and proteinuria) will be analyzed for correlation with the incidence of ARN. Demographic variables including age and race will be analyzed in contingency tables using Fisher's exact test to ascertain if they are significant for the primary outcome.

There is no data at all in the literature for the incidence of ARN with rivaroxaban or apixaban and we short-listed that number (40) based on the reported incidence for warfarin (17-37%). We are selecting the patients at highest risk (elderly, CKD) for anticoagulation-related nephropathy (ARN) and we expect that the incidence we obtain will be the highest for the population we are studying.

In terms of precision, we will calculate confidence intervals of the proportional incidence using Stata (command line `cii 40 (incidence)`). If the incidence is zero, Stata calculates the 95% confidence interval based on our sample size as 0-9%. If we only find 2 cases of ARN, Stata calculates the point estimate incidence at 5% with 95% confidence interval as 0.6% - 17%, If we find 10 cases of ARN, Stata calculates the point estimate incidence as 25% with 95%

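### The stated precision and the interval command assume 40 known outcomes, which conflicts with the rule deleting censored participants and would bias incidence low if applied despite loss

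*Protocol*

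**What the plan says.** In the Protocol's data analysis plan (Data Management, item ii) the primary outcome is the incidence of ARN: "This incidence will be expressed as a percentage". For the interval, "we will calculate confidence intervals of the proportional incidence using Stata", and the command given in brackets carries 40 as its sample size (`cii 40`). Three worked examples follow, all on 40:

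- No cases: "Stata calculates the 95% confidence interval based on our sample size as 0-9" percent.
- Two cases: "Stata calculates the point estimate incidence at 5% with 95% confidence interval as 0.6% - 17" percent.
- Ten cases: an estimate of 25%, with an interval of 13% to 41%.

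The enrolment target in section 5(b)(i) is the same number: "Total number of subjects planned to be enrolled in the study at AEHN site(s): 40". There is no allowance for loss.

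Two other parts of the Protocol bear on the denominator. Under Withdrawal of Subjects, item i (and Study Endpoints, item ii), a participant whose anticoagulation is withdrawn for a clinical reason is censored. Item ii of the same section then removes all of a censored participant's data from the participant list and the database. Under Human Research Methods, item ii, creatinine and urinalysis are repeated at months 1, 2, 3 and 6, and a case can be recognised only from a creatinine rise followed by a work-up.

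**The concern.** Two things do not fit together.

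First, a fixed 40 and a delete-on-censoring rule cannot both be applied. Once one participant is deleted, the database holds fewer than 40, and the command and the quoted precision no longer describe it. Deletion also discards ARN-free time, or an ARN case, already observed before anticoagulation was withdrawn.

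Second, a participant still on the drug who misses the later draws or is lost has an unknown outcome after the last draw attended. If the command is run as written, that person stays in the denominator and cannot enter the numerator. The reported incidence is then too low and its interval too narrow. The error runs toward the study's hypothesis that incidence is lower than reported for warfarin. The upper limit with zero or few cases matters most, because the data analysis plan intends to read a negative result as evidence of very low risk in the general population.

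**Working it through.** **Inputs from the Protocol.** n = 40 (section 5(b)(i) and the data analysis plan); examples with 0, 2 and 10 cases; draws at months 1, 2, 3 and 6.

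**Assumptions, because the Protocol gives no figures.** Loss of 10%, 20% or 30% by six months, a quarter of it before each draw and unrelated to ARN; 70% of ARN found by month 2; true six-month risk of 20%.

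**Step 1: reproduce the stated intervals.** The exact (Clopper-Pearson) 95% limits for x cases in n are the 2.5% quantile of Beta(x, n-x+1) and the 97.5% quantile of Beta(x+1, n-x). For x = 0 the lower limit is 0 and the upper limit is 1 - 0.025^(1/n).

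| Cases / n | Exact 95% interval | Protocol |
|---|---|---|
| 0/40 | 0-8.81% | 0-9% |
| 2/40 | 0.61-16.92% | 0.6-17% |
| 10/40 | 12.69-41.20% | 13-41% |

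All three agree, so the arithmetic is right for 40 known outcomes.

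**Step 2: the same interval with fewer evaluable.**

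| Cases | n = 40 | n = 36 (10% loss) | n = 32 (20% loss) | n = 28 (30% loss) |
|---|---|---|---|---|
| 0 | 0-8.8% | 0-9.7% | 0-10.9% | 0-12.3% |
| 2 | 0.6-16.9% | 0.7-18.7% | 0.8-20.8% | 0.9-23.5% |
| 10 | 12.7-41.2% | 14.2-45.2% | 16.1-50.0% | 18.6-55.9% |

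**Step 3: bias if the divisor stays 40.** Let p be the true risk, L the total loss and f(k) the share of ARN arising at draw k (k = 1 to 4). A case at draw k is seen with probability 1 - kL/4, so the expected value of x/40 is p × (1 - L × m/4), where m is the sum of k × f(k).

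Splitting the early 70% as 35% and 35%, and the late 30% as 15% and 15%, gives m = 0.35 + 0.70 + 0.45 + 0.60 = 2.10. The expected value is then p × (1 - 0.525L):

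- L = 10%: 20% × 0.9475 = 18.95%
- L = 20%: 20% × 0.895 = 17.9%
- L = 30%: 20% × 0.8425 = 16.85%

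The split within each period is a further assumption. If the 70% all falls at month 1 and the rest at month 3, m = 0.7 + 0.9 = 1.6, and 30% loss gives 20% × 0.88 = 17.6%. If it falls at months 2 and 6, m = 1.4 + 1.2 = 2.6, and 30% loss gives 20% × 0.805 = 16.1%.

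A simulation of 40 participants under the 35/35/15/15 split (8,000 replicates per setting, no deaths) agreed with these values to about 0.1 point. On the same data Kaplan-Meier, censoring at the last draw attended, averaged 19.9% to 20.0%.

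**Step 4: width.** Take the limiting case in which loss precedes every draw and the rate among those seen is 25%. With 20% loss, 8/32 = 25.0% has interval 11.5-43.4% (31.9 points wide). The same 8 cases over 40 are reported as 20.0%, about 9.1-35.6% (26.6 points wide).

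**The case against.** The strongest reply is that the 40 is a planning figure. It stands in a paragraph about precision, answering a form prompt that also asks how the sample size was chosen, and the outcome sentence names no denominator. A reader might infer that the Protocol counts lost participants as ARN-free. It does not say so. For those whose anticoagulation is withdrawn it does the opposite, since deletion takes them out of numerator and denominator alike, and voluntary withdrawals may be meant to go the same way. This part of the reply stands: scoring as non-cases follows only if the command is applied literally to missed draws and other loss.

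A reader might also argue that deaths between draws hide cases, because the background cites a study that "showed a 65% increase in mortality in patients with ARN". The documents do not support that step. The figure comes from a retrospective warfarin cohort and is reported alongside 5-year survival, so it says little about deaths within six months on these drugs.

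It can further be said that missing-data rules may sit in a separate analysis plan, that a proportion with an exact interval is a normal result for a 40-person descriptive study, and that the bias at 10-20% loss is only one to two points against an interval for 8/40 running from about 9% to 36%. The Protocol also pays $10 per draw and requires willingness to attend follow-up, which should limit loss. These points limit the size. They do not remove the conflict between a stated command with n = 40 and a stated deletion rule, nor the fact that the promised precision needs every enrolled participant to be evaluable.

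**Conclusion.** The point holds in a limited form. Two parts rest on the Protocol's text and on reproduced arithmetic: the stated precision is a best case, and the fixed 40 cannot coexist with deletion of censored participants. The downward bias is conditional on the command being run literally with incomplete follow-up. Its size depends on assumed loss and timing: for a true 20%, about 19%, 18% and 17% at 10%, 20% and 30% loss (16.1% to 17.6% at 30% loss under the other timings tried). The zero-case upper limit rises from 8.8% to 9.7-12.3% over the same losses. This is modest beside sampling error, but it runs toward the hypothesis and is cheap to avoid. It should be corrected, though it does not undermine the study.

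**What to change.** 1. Reconcile the data analysis plan with Withdrawal of Subjects, items i and ii: keep a censored participant's data up to the time of censoring.
2. Make the primary estimate the six-month cumulative incidence of ARN over the four draws, censoring at the last draw attended. Use an Aalen-Johansen estimate with death without ARN as a competing event (Kaplan-Meier if there are no deaths), with its 95% interval.
3. As a check, report cases over the actual number evaluable with an exact interval, and a worst case counting those lost as cases.
4. Keep the precision examples for 40, labelled as assuming complete follow-up, and add a set for a smaller number. At an assumed 32: 0-11% for 0 cases, 0.8-21% for 2, 11-43% for 8.

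This needs no new visits, samples or participants. The cost is slightly more analysis work and stated intervals that are slightly wider.

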The clinical trials that compared the NOACs to warfarin did not specifically study ARN and did not repeat creatinine and urinalysis testing in the first two to three months of therapy to establish possible ARN diagnosis [15-20]. In most of these studies, only baseline creatinine and creatinine levels 6 to 12 months later were analyzed, hence it is possible that ARN was under-diagnosed as most cases of ARN are detected in the first eight weeks of therapy. Our study aims to accurately capture ARN cases by making these measurements monthly in the first three months of starting the anticoagulant.

This study is pivotal because it will for the first time, define the incidence of ARN in patients on rivaroxaban or apixaban therapy. If we find that ARN incidence in patients started on rivaroxaban or apixaban is less than that seen with warfarin, this can help support evidence that this NOAC is safer for the kidneys compared to warfarin and this data can enable us make evidence based decisions regarding the continued use of the medication to help our patients. If on the other hand we find that the medication leads to ARN, then we will be contributing important post-marketing surveillance data that can also help us make safety decisions about the use of the medication in the future.

INNOVATION

Previous studies on ARN have utilized retrospective study designs which have many epidemiological pitfalls including the cause versus effect bias and the inability to ascertain relative risk [1]. Our study is unique because we intend to utilize a prospective epidemiological design to study this renal complication, a first in the study of ARN. This is important because ARN is a diagnosis of exclusion and hence a prospective study is able to more accurately define cases of the condition compared to the assumptions that are made in retrospective studies where further work up cannot be done in retrospect.

This will be the first epidemiological study focused on ARN in a NOAC. Even though NOACs are new, they are becoming ubiquitous and a mainstay in clinical practice and not just an alternative to warfarin. For example, the recent CHEST guidelines recommend them as first line therapy in the treatment of venous thromboembolism [8]. Hence it will be important to clearly delineate their effects on the kidneys.

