Screening will be also be carried out by a query on the electronic medical record with a confidential report generated weekly by the Einstein's AECIS which will contain all rivaroxaban and apixaban prescriptions ordered by electronic scripts. Investigators and co-investigators will review the medical records of patients on the list to determine if they meet the inclusion criteria for the study.

Identified patients will be given a written description about the study and [name] (principal investigator) will be notified. All identified patients will have their medical records/chart reviewed by [name] to determine eligibility for the study. If appropriate, he will then contact them by phone and arrange a meeting to discuss the study protocol, answer any questions and complete the consent process

- ii. Describe the criteria that define who will be included or excluded in your final study sample:

Inclusion Criteria

- Age \geq 60 years
- GFR \leq 90 ml/L based on creatinine clearance
- Participant has been initiated on long term anticoagulation with rivaroxaban or apixaban for atrial fibrillation within four weeks of recruitment
- Participant is willing to comply with all aspects of the protocol, including adherence to medical therapy and follow-up visit
- Participant is willing to give written informed consent

Exclusion Criteria

- History of blood dyscrasias or active bleeding,
- History of hematuria
- Patients on dialysis

c. Study Timelines:

- i. Duration of an individual subject's participation in the study: 6 months
- ii. Time period anticipated to enroll all study subjects or to complete chart review: 4 months
- iii. Estimated overall study duration (*i.e. from initiation to completion of primary analyses*): 12 months

d. Study Endpoints:

- i. Describe the primary and secondary study endpoints (*i.e. the outcome(s) that the study is designed to evaluate*):

Primary endpoint - Incidence of ARN is the primary outcome of this study and this is based on a documentation of AKI (defined as an increase in baseline serum creatinine \geq 0.3 mg/dL), in the absence of any other obvious etiology for the AKI identified after a standard clinical evaluation and work up by the patient's primary care physician, cardiologist or nephrologist. This incidence will be expressed as a percentage.

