confidence interval as 13% to 41%, etc. Our sample is elderly, CKD subjects at higher risk hence we expect a higher incidence than in the normal population, hence a negative result will suggest very low risk in the general population.

- iii. Describe where and how data will be stored locally: Data will be stored in password protected spreadsheets on the Einstein computer network.
- iv. Specify how long data will be stored locally: 6 years after publication of the study
- v. Specify who will have access to the data locally: The research team members.
- vi. Describe process that will be followed to ensure accuracy of collected data: All data will be checked twice upon entering it into the database to ensure accuracy. All calculations and statistical tests will be confirmed by both members of the team.
- vii. Will data be sent out or received: No Yes
 - a. Who is responsible for receipt or transmission of the data? N/A
 - b. How will the data be transported? N/A

h. Provisions to monitor the data for the safety of subjects (Required only when Human Research involves more than minimal risk):

- i. Describe plans to periodically evaluate the data collected regarding both harms and benefits to determine whether subjects remain safe. Include what data will be reviewed, who will review the data and when the data will be reviewed:

This research has no additional risk above and beyond that of a blood draw and urine collection. Blood draws for serum creatinine assay will be performed by a trained phlebotomist using standard techniques. Any problems encountered during blood draws will be reported to the research staff and will be reviewed by the entire research study team as soon as they occur to determine if and when the event needs to be reported to the IRB, and if the protocol and/or consent document require modification. Each safety data will be reviewed by at least 2 members of the research team and all events will be reviewed after every 10 patients are recruited.

i. Withdrawal of Subjects:

- i. Describe the anticipated circumstances under which subjects will be withdrawn from the research without their consent: Subjects will be censored from the study if anticoagulation is withdrawn for any clinical reason

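### A negative result is extended to the general population, although the protocol neither shows nor can test that treated patients outside its entry criteria have an average risk no higher than the cohort's

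*Protocol*

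**What the plan says.** The argument stands at the end of the data analysis plan (Study Design, part g, Data Management, item ii). The plan says that patients at highest risk are being selected on age and CKD and that the incidence found should therefore be the highest. It then concludes: "we expect a higher incidence than in the normal population, hence a negative result will suggest very low risk in the general population".

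The entry criteria (Study Design, part b, item ii) require age 60 or over, GFR at or below 90, and this: "Participant has been initiated on long term anticoagulation with rivaroxaban or apixaban for atrial fibrillation within four weeks of recruitment". They exclude "History of blood dyscrasias or active bleeding", "History of hematuria" and patients on dialysis.

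Two other places describe the setting more widely. The Innovation part of section 3 illustrates the spread of these drugs with another indication: "the recent CHEST guidelines recommend them as first line therapy in the treatment of venous thromboembolism". Section 5(a) gives the target population as "Elderly patients with CKD who have recently been started on Rivaroxaban or Apixaban", with no indication named.

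**The concern.** The reassurance is drawn from age and kidney function only. The entry criteria also select on indication and on several histories, and the argument does not mention them. No section limits the conclusion to patients like those enrolled, or argues that the patients left out are at no higher risk.

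Hematuria shows the gap most clearly. The protocol singles it out, with proteinuria, as a urinalysis finding to be correlated with ARN. Yet patients with a history of it cannot enter, and the study will say nothing about their risk.

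At stake is the reach of the safety message. The Significance part of section 3 says that a low incidence could support the view that the drug is safer for the kidneys than warfarin and could inform its continued use. The section on sharing results sends the findings to participants and to publication. A count of zero or a few, read as the plan reads it, would reassure patients and prescribers about groups that the study did not observe.

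**Working it through.** **Inputs.** Planned size: "Total number of subjects planned to be enrolled in the study at AEHN site(s): 40". Intervals stated in the data analysis plan: 0-9% for 0 cases, 0.6-17% for 2, 13-41% for 10. Warfarin figures: 16-37% in the Background, 17-37% in the data analysis plan. The documents give neither the ineligible share of treated patients nor their ARN risk.

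**1. The plan's own figures.** Exact binomial (Clopper-Pearson) 95% limits at n = 40:
- 0/40: upper limit 1 − 0.025^(1/40) = 0.0881, so 0-8.8%
- 2/40: 0.6-16.9%
- 10/40: 12.7-41.2%

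All three agree with the protocol after rounding. They describe risk in patients like the 40.

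**2. What the extension needs.** Let p_E be the risk in eligible-type patients, p_I the average risk in all other treated patients, and s the share of the latter. Overall risk is

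P = (1 − s) × p_E + s × p_I.

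For s above zero, P ≤ p_E exactly when p_I ≤ p_E. This is a condition on the average. It does not require every subgroup to be at or below the cohort's risk.

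**3. What the study can say about p_I.** The probability of 0 cases in 40 is (1 − p_E)^40, which does not contain p_I. No result in this cohort can confirm or refute the condition, and a larger sample under the same criteria would not change that.

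**4. What the protocol says about p_I.** Taking the patients left out in turn:
- Under 60, or GFR above 90: the age and CKD argument applies and points to lower risk.
- Treated for another indication: no statement on ARN risk.
- History of hematuria: no statement on risk. Hematuria on urinalysis is only a candidate correlate.
- Blood dyscrasia, active bleeding, dialysis: listed as exclusions, with no statement on ARN risk.

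The stated argument therefore covers the first group only. p_I averages over all of them.

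**5. Illustration.** Both s and p_I are assumed here: s from 10% to 50%, p_I from 5% up to the top warfarin figure of 37%.

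With p_E = 0, P = s × p_I:
- 0.10 × 0.05 = 0.5%
- 0.20 × 0.37 = 7.4%
- 0.50 × 0.37 = 18.5%

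With p_E at the upper limit for 0/40 (8.81%):
- 0.50 × 0.0881 + 0.50 × 0.05 = 6.9%
- 0.50 × 0.0881 + 0.50 × 0.37 = 22.9%

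In this second setting, overall risk can fall below or rise above the cohort's limit, depending only on whether p_I is below or above p_E.

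**The case against.** The strongest reply is that the sentence is modest and its direction sensible. It says that a negative result will suggest low risk, not prove it. It contrasts elderly CKD patients with a normal population, which can be read as people without those risk factors, and for them the argument is reasonable. The Background names CKD, older age, diabetes and hypertension as risk factors; it does not name indication, hematuria history, dyscrasia or bleeding. A small higher-risk subgroup would also be compatible with a low population average. Nearly every study has exclusions, so a general caveat about external validity needs some specific hook.

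Much of this stands, and it rules out stronger readings that a reader might infer:
- That the exclusions remove high-risk patients. The documents do not say so. Hematuria is only to be analysed for correlation, and the exclusion concerns past hematuria while the analysed variable is a urinalysis measurement.
- That any history of bleeding is excluded. The criterion is most naturally read as active bleeding.
- That patients treated for venous thromboembolism are at higher risk. The protocol mentions that indication only as an example of use.
- That section 5(a) contradicts the entry criteria. It is a short form field that omits the indication.

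What does not stand is the defence of the sentence itself. It draws a consequence for the general population from age and CKD alone. The hedge softens the strength of the claim but does not narrow whom it covers, and nothing elsewhere narrows it.

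**Conclusion.** The concern holds as one of unsupported scope. The plan fixes in advance a conclusion wider than its cohort can carry, because it rests on an average-risk condition for unenrolled patients that is neither argued beyond age and CKD nor testable in the study. It does not follow that the conclusion is false; risk outside the entry criteria may be lower.

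No size can be derived from the documents. The range of 0.5% to 18.5% rests on zero risk in eligible patients and on two assumed inputs. Its low end would fit the plan's own wording and its high end would not. It shows only that 0 of 40 leaves the question open.

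The endpoint and the planned intervals are unaffected, and the exclusions can stand. Separately from this point, the upper limit of 8.8% for 0/40 means that even for eligible patients a zero count should be reported with its interval.

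**What to change.** Replace the sentence at the end of the data analysis plan with:

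*A result with no or few cases, reported with its 95% confidence interval (0-9% for 0/40), applies to patients who meet the entry criteria: age 60 or over, treated for atrial fibrillation, meeting the renal criterion, without a history of hematuria or blood dyscrasia, active bleeding or dialysis. It does not establish the risk in patients treated for other indications or in the excluded groups.*

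Naming atrial fibrillation in section 5(a) and in the objective in section 2 would be optional tidying; the point does not depend on it.

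The change is to protocol wording only. Eligibility, visits, sample size and calculations stay as they are. The downside is a narrower claim from a negative result.

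### The planned reading of a negative result as very low general-population risk goes beyond the protocol's own interval, which for zero cases in 40 reaches about 9%

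*Protocol*

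**What the plan says.** The data analysis plan (Protocol, Study Design, Data Management, item ii) reports incidence as a percentage with a Stata confidence interval, using a command with the denominator written in as 40. Its first example is the best case: "If the incidence is zero, Stata calculates the 95% confidence interval based on our sample size as 0-9" percent. Two cases give 0.6 to 17%, and ten give 13 to 41%.

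The same item then interprets the result in advance. The premise is "Our sample is elderly, CKD subjects at higher risk hence we expect a higher incidence than in the normal population", and the conclusion is "hence a negative result will suggest very low risk in the general population". Neither a negative result nor very low risk is given a definition.

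The sample is described as "Elderly patients with CKD who have recently been started on Rivaroxaban or Apixaban" (section 5, item a) and as "40 high risk patients who are recently started on either apixaban or rivaroxaban" (section 1, abstract). The inclusion criteria (Study Design, item b.ii) require age 60 or over and a GFR at or below "90 ml/L based on creatinine clearance" (units as printed). CKD is not defined anywhere.

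Under Withdrawal of Subjects (Study Design, item i), patients whose anticoagulant is stopped for a clinical reason are censored, and all their data are taken out of the study database.

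**The concern.** The two statements stand next to each other and do not fit. The first says that the most favourable outcome leaves incidences up to about 1 in 11 compatible with the data in the patients studied. The second reads a negative outcome as very low risk in a wider population that was not studied.

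The link between them is the idea that the sample is at higher risk. That is reasonable in direction but supplies no number. It lets a reader say that the general population's risk is no higher than the cohort's. It does not say how much lower.

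This is a safety conclusion written down before the data exist. The Significance section says that the results may inform decisions about continued use of these drugs, and the section on sharing results promises participants a handout with the conclusions. An over-reassuring reading could therefore reach both prescribers and patients.

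**Working it through.** **Inputs from the protocol.** N = 40; 95% interval from Stata; stated intervals for 0, 2 and 10 cases; warfarin range 16 to 37% (Background) or 17 to 37% (data analysis plan). The exact binomial (Clopper-Pearson) method is assumed, because it reproduces all three stated examples.

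**Step 1: reproduce the protocol's figures.** For zero cases the two-sided 95% upper limit is 1 − 0.025^(1/N). With N = 40 this is 1 − 0.025^(1/40) = 8.81%, which rounds to the stated 9%. The same method gives 0.61 to 16.9% for two cases and 12.7 to 41.2% for ten, matching the protocol.

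**Step 2: what zero cases can and cannot tell apart.** The chance of zero cases in 40 is (1 − p)^40 at true cohort incidence p. The values of p are assumed.

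| True incidence p | Chance of 0/40 |
|---|---|
| 1% | 67% |
| 2% | 45% |
| 3% | 30% |
| 5% | 13% |
| 7% | 5.5% |
| 16% (low end for warfarin) | 0.09% |

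Zero cases would be strong evidence against 16%, but would not separate 1% from 3%.

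**Step 3: carry the limit to the general population.** Let R be the ratio of cohort risk to general-population risk. The ceiling for the general population is then 8.8%/R. The protocol's premise amounts to R above 1 with no value attached:

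- R = 1: 8.8%
- R = 2 (assumed): 8.8/2 = 4.4%
- R = 4 (assumed): 8.8/4 = 2.2%

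Reaching 1% would need R = 8.8. Without R, only the ceiling of about 9% is supported.

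**Step 4: other meanings of negative.** The upper limit at N = 40 is 13.2% for one case and 16.9% for two. Any reading other than zero cases therefore weakens the conclusion.

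**Step 5: the denominator.** If patients are removed under the withdrawal rule, the zero-case limit rises. For assumed numbers analysed:

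- N = 36: 9.7%
- N = 32: 10.9%
- N = 30: 11.6%

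The limit then describes only patients who stayed in the analysis.

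**Step 6: the premise against the criteria.** The elderly half of the description is secured by age 60 or over. The CKD half is not secured by a definition: the only renal inclusion criterion is GFR at or below 90. How far the enrolled patients exceed general-population risk will depend on the creatinine clearances actually recruited.

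**The case against.** The best defence is that the sentence is modest. It says only that a negative result will suggest low risk, the 0 to 9% interval is printed in the same item, and no endpoint, test or decision rule depends on the remark. The sentence also concerns a population that the protocol believes to be at lower risk than the cohort, so the 9% limit is not directly its limit. These points stand, and they keep the severity down. They do not close the gap, because the step from about 9% to very low still needs a risk ratio that is not given.

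Four stronger readings are tempting, and the protocol does not support them.

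- *That 9% is itself shown not to be very low.* The protocol sets no threshold, so that would be a judgement.
- *That the study must be enlarged.* Bringing the zero-case limit to an assumed 5%, 2% or 1% would take 72, 183 or 368 patients, from ln(0.025)/ln(1 − p) rounded up. With no threshold stated, none of these is a requirement. The estimate that "We estimate that around 100 patients meeting our criteria are started on Apixaban or Rivaroxaban in a six-month period" does not settle whether more could be recruited.
- *That one case would also count as negative.* This needs a rule that the protocol does not state, such as an upper limit below the warfarin range. Under such a rule the answer turns on which figure is used: against 16% only zero or one case qualifies, while against 17% two cases (16.9%) do as well.
- *That zero cases could not support a risk below warfarin's.* Numerically they would, since 8.8% is below 16%.

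**Conclusion.** The pre-stated conclusion goes beyond the protocol's own interval. Zero cases in 40 would be compatible with an incidence up to 8.8% in patients like those analysed. If cohort risk is at least general-population risk, that same ceiling applies there, and nothing in the protocol lowers it further. The limit rises if fewer than 40 are analysed or if any case occurs.

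The finding assumes the exact binomial interval, which matches the stated examples. The probabilities in step 2, the ratios in step 3 and the reduced denominators in step 5 are illustrations, not protocol figures.

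Severity is minor to moderate. The arithmetic is right and the planned estimate with its interval is sound. What needs correcting is one sentence of interpretation and the description of the sample that supports it. A reader should not infer that the eligibility criteria are wrong, only that the CKD label says more than they secure.

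**What to change.** Replace the sentence in the data analysis plan with:

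*A negative result means zero cases. Zero cases among the N patients analysed would be compatible with an incidence up to the exact 95% upper limit (about 9% if N = 40, higher if fewer are analysed) in patients like those retained in the analysis, and does not by itself show very low risk in the general population. For any other count the exact interval is reported.*

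In addition:

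- Use the number actually analysed in the interval command, not a fixed 40.
- State that patients whose data are removed under the withdrawal provisions are not covered by the limit.
- Describe the sample by its actual criteria (age 60 or over, GFR at or below 90) wherever it is now called CKD, high risk or highest risk, and report the distribution of baseline creatinine clearance.

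The cost is a few wording changes and one descriptive row from baseline data already collected. Eligibility, sample size and visits do not change. The price is a more modest claim.
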